## **6 STUDY PRODUCT**

### **6.1 Regimen**

Each participant will receive one vaginal film.

### **6.2 Administration**

After eligibility is confirmed, site staff will randomize the participant to the timing of Visit 3 and retrieve the study product from the Pharmacy. Participants will be counselled thoroughly on product administration and then handed the film in its packaging. The participant will attempt to insert the film while a site staff member stands behind a curtain to maintain privacy. Should the participant have any concerns or questions, the site staff member will be readily available. Immediately after the participant attempts insertion, the site clinician will do a quick inspection of the external genitalia to assess for proper placement. If the film is visible outside of the vaginal introitus, the clinician will return to the pharmacy to retrieve a second dose of the vaginal film. The clinician will then remove visible film, insert a speculum, remove visible film from inside the vagina, and place a second film in the proximal third of the vagina using a forceps instrument.

### **6.3 Study Product Formulation**

A two inch by two inch (2" x 2") film containing no active pharmaceutical ingredient will be used. This placebo film is a cellulose based film containing hydroxypropyl methyl cellulose (HPMC) (E5 and K4M), hydroxyethyl cellulose (HEC), hydroxypropyl cellulose (HPC), Eudragit® (Ammonio Methacrylate Copolymer Type B), propylene glycol and polyethylene glycol 400. Placebo films will be manufactured by CMO under cGMP using hot melt extrusion and clinical trial material will be subjected to GMP stability program by the contract manufacturer.

### **6.4 Study Product Supply and Accountability**

Packaged study product is being provided to the Magee-Womens Hospital Pharmacy. All study product will be available to the study staff through the Magee Pharmacy.

The Magee research pharmacist will maintain complete records of all study products received for this protocol and dispensed to participants. Additional documentation will be required for study product returns, destruction (if applicable) and other related issues as outlined in instructions for DAIDS clinical trials. All unused study products must be returned to the Pharmacy.

The film is packaged into a foil-lined pouch and stored at room temperature. Product has R&D stability for 6 months.

## **6.5 Study Product Dispensing**

Study products will be dispensed only to enrolled participants upon receipt of a written prescription signed by an authorized prescriber.

## **6.6 Concomitant Medications**

Enrolled study participants may use concomitant medications during study participation. All concomitant medications, over-the-counter preparations, vitamins and nutritional supplements, recreational drugs, and herbal preparations will be recorded on the concomitant medications log form.

All participants will be counseled to avoid the use of spermicide and other non-study vaginal products (other than tampons during menstruation and female condoms) while participating in the study. Participants who report use of these products will be counseled regarding the use of alternative methods, but reported use of these products does not require any change in study product administration or follow-up procedures. Condoms provided by study staff will not be coated with any type of spermicide.

# **7 STUDY PROCEDURES**

This section describes visit-specific study procedures.

## **7.1 Pre-Screening**

As part of participant outreach and recruitment strategies, study staff may pre-screen potential study participants (e.g. via telephone). During these interactions, study staff may explain the study to participants and ascertain elements of presumptive eligibility, to be confirmed at an on-site screening visit. If the participant is eligible based on a screening script her name and appointment time will be placed on the script. If she signs consent, the telephone script will then become part of her research record. If she does not sign consent, the form will be de-identified.

## **7.2 Visit 1: Screening Visit**

Screening may take place up to 45 days prior to Enrollment. Screening procedures may occur over several visits. A combined written informed consent for screening and enrollment will be obtained before any screening procedures are initiated. For participants who do not meet the eligibility criteria, screening will be discontinued once ineligibility is determined.

The table below outlines procedure to take place at the Screening Visit.

**Table 2: Visit 1 Procedures**

VISIT 1: SCREENING VISIT	
Component	Procedure/Analysis
ADMINISTRATIVE	
 
• Written Informed Consent
 
• Assign Study Number (PTID)
 
• Review Eligibility
 
• Collect Contact Information
 
• Visit Questionnaire
 
• HIV Pre-/Post-Test Counseling
 
• Screening Results
 
• Abstinence/Condom Counseling (& distribution prn)
 
• Schedule Next Study Visit, prn
 
• Participant Reimbursement
 

URINE	
 
• Pregnancy test
 
• Urine dipstick, as clinically indicated
 

SALIVA	
 
• Rapid HIV
 

BLOOD	
 
• Confirmatory HIV, as clinically indicated
 

VAGINAL	
 
• pH
 
• Wet Mount, as clinically indicated
 
• Trichomonas (NAAT)
 
• Future Use
 

CERVICAL	
 
• GC/CT (NAAT)
 
• Future Use
 

CVL	
 
• Levels of antiviral activity
 
• Lectin microarray
 
• Levels of glycoproteins and mucins
 
• Levels of cytokines & innate immunity factors
 
• Eudragit® level
 

PHYSICAL EXAM	
 
• Physical Exam
 
• Vital Signs (BP)
 
• Height & Weight
 

PELVIC EXAM	
 
• Bimanual Exam, as clinically indicated
 
• External Genital & Speculum Exam
 

### 7.3 Visit 2: Enrollment

Subjects who meet the inclusion and exclusion criteria following the Screening Visit may schedule an Enrollment Visit. Care will be taken to schedule the Enrollment visit at a time when the participant is not expecting to be actively bleeding or anticipating her menses within 14 days.

Before performing any enrollment procedures, study staff will confirm eligibility. The participant will undergo a pelvic examination. Pelvic specimens as described below will be collected and the study staff will assess for bleeding. If no bleeding or other exclusionary findings are evident, the participant will then be randomized to the timing of Visit 3. The act of randomization is considered the act of enrollment for this study. Subjects with menses like vaginal bleeding at the Enrollment visit will not be randomized/enrolled at that time. These subjects may be rescheduled if vaginal bleeding resolves before 45 days from Screening have elapsed. If vaginal

bleeding does not resolve during the window period, and the subject expresses interest in enrollment for the study, she may be offered a rescreening attempt.

After eligibility is confirmed, the clinician will go to the Pharmacy to obtain the study product. Participants will be counselled thoroughly on product administration and then handed the film in its packaging. The participant will attempt to insert the film while a site staff member stands behind a curtain to maintain privacy. Should the participant have any concerns or questions, the site staff member will be readily available. Immediately after the participant attempts insertion, the site clinician will do a quick inspection of the external genitalia to assess for proper placement. If the majority of the film is visible outside of the vaginal introitus, the clinician will return to the pharmacy to retrieve a second dose of the vaginal film. The clinician will then remove visible film, insert a speculum, remove visible film from inside the vagina, and place a second film in the proximal third of the vagina using a forceps instrument. After film placement, participants will be scheduled for Visit 3. When Visit 3 occurs will be determined by randomization (3, 7, 10 or 14 days).

**Table 3: Visit 2 Procedures**

VISIT 2: ENROLLMENT – DAY 0 (Day 1 of Product Use)	
Component	Procedure/Analysis
ADMINISTRATIVE	
 
• Review/Confirm Eligibility
 
• Collect/Update Contact Information
 
• Visit Questionnaire
 
• Screening Results
 
• Abstinence/Condom Counseling (& distribution prn)
 
• Assess/Document Adverse Events
 
• Schedule Next Study Visit
 
• Participant Reimbursement
 

ACCEPTABILITY	
 
• Acceptability Questionnaire
 

URINE	
 
• Pregnancy test
 
• Urine dipstick, as clinically indicated
 

VAGINAL	
 
• pH
 
• Wet Mount, as clinically indicated
 
• Gram Stain
 
• Quantitative Vaginal Culture
 
• Quantitative PCR for microbiota
 
• Future Use
 

CERVICAL	
 
• Future Use
 

PHYSICAL EXAM	
 
• Physical Exam, as clinically indicated
 
• Vital Signs (BP)
 

PELVIC EXAM	
 
• Bimanual Exam, as clinically indicated
 
• External Genital & Speculum Exam
 
• Post-insertion External Genital Exam
 
• Repeat Speculum Exam, prn
 

RANDOMIZATION	
 
• Randomization to timing of V3
 

STUDY PRODUCT	
 
• Study Product Distribution
 
• Participant Self-Inserted (1st attempt)
 
• Clinician-inserted (2nd attempt), prn
 

## 7.4 Visit 3: Follow-Up Visit

The timing of Visit 3 will be determined through the randomization process. All participants will be randomized to return either 3,7,10, or 14 days after film insertion. Visit 3 procedures are outlined in Table 4. The windows around these study visits are as follows:

Day 3 (days 2-4)

Day 7 (days 6-8)

Day 10 (days 9-11)

Day 14 (days 12-16)

**Table 4: Visit 3 Procedures**

VISIT 3: FOLLOW-UP VISIT – 3, 7, 10, 14 DAYS POST FILM INSERTION	
Component	Procedure/Analysis
ADMINISTRATIVE	
 
• Collect/Update Contact Information
 
• Visit Questionnaire
 
• Abstinence/Condom Counseling (& distribution prn)
 
• Assess/Document Adverse Events
 
• Schedule Next Study Visit
 
• Participant Reimbursement
 

ACCEPTABILITY	
 
• Acceptability Questionnaire
 

URINE	
 
• Pregnancy test
 
• Urine dipstick, as clinically indicated
 

VAGINAL	
 
• pH
 
• Wet Mount, prn
 
• Trichomonas (NAAT), as clinically indicated
 
• Gram Stain
 
• Quantitative Vaginal Culture
 
• Quantitative PCR for microbiota
 
• Future Use
 

CERVICAL	
 
• GC/CT (NAAT), as clinically indicated
 
• Future Use
 

CVL	
 
• Levels of antiviral activity
 
• Lectin microarray
 
• Levels of glycoproteins and mucins
 
• Levels of cytokines & innate immunity factors
 
• Eudragit® level
 

PHYSICAL EXAM	
 
• Physical Exam, as clinically indicated
 
• Vital Signs (BP)
 

PELVIC EXAM	
 
• Bimanual Exam, as clinically indicated
 
• External Genital & Speculum Exam
 

## 7.5 Visit 4: Follow-Up Visit 21 Days Post Enrollment

The final scheduled visit will be 21 (18-25) days after the Enrollment Visit.

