## **5.5 Exclusion Criteria**

Women who meet any of the following criteria by participant report will be excluded from the study. Of note, the study is limited to premenopausal women with an intact uterus because the mucosal immune environment differs substantially between pre- and post- menopausal women. Therefore, inclusion of post-menopausal women would introduce heterogeneity into the population.

- 1.) Menopause (as defined as amenorrhea for one year or more without an alternative etiology)
- 2.) Hysterectomy
- 3.) Participant report of any of the following:
  - a) Known adverse reaction to any of the study products (ever)
  - b) Known adverse reaction to latex (ever)
  - c) Non- therapeutic injection drug use in the 12 months prior to Screening
  - d) Surgical procedure involving the pelvis in the 90 days prior to enrollment (includes dilation and curettage or evacuation, and cryosurgery; does not include cervical biopsy for evaluation of an abnormal pap smear)
  - e) Participation in a drug, spermicide and/or microbicide study in the 30 days prior to enrollment or anticipated participation in an investigational drug study until completion of the study
  - f) Currently pregnant or pregnancy within 42 days prior to enrollment
  - g) Currently lactating
  - h) Use of a diaphragm, NuvaRing®, or spermicide for contraception
  - i) Internal vaginal use of any device or product (except tampons) in the 48 hours prior to enrollment
- 4.) Urogenital infection or suspected infection within 14 days of enrollment including: symptomatic candidiasis, trichomonas vaginalis, and symptomatic bacterial vaginosis; or cervical infection, including *N. gonorrhoeae* (GC), *C. trachomatis* (CT), or mucopurulent cervicitis; syphilis; HSV lesions, or other sores (Note: seropositive HSV without active lesions will not be excluded); acute pelvic inflammatory disease; urinary tract infection; recent exposure to a partner with GC, CT, Trichomonas, syphilis, or NGU

- 5.) Antibiotic or antifungal therapy (vaginal or systemic) within 14 days of enrollment
- 6.) As determined by the PI, has any significant uncontrolled active or chronic cardiovascular, renal, liver, hematologic, neurologic, gastrointestinal, psychiatric, endocrine, respiratory, immunologic disorder or infectious disease
- 7.) Menses-like bleeding at the time of the Enrollment visit\* or expected menses-like bleeding within 14 days of the Enrollment visit  

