#### Exploratory: Vaginal Microenvironment

Given that there is no non-product use arm, participants will serve as their own control. Assessment of baseline microenvironment will take place during the enrollment visit with the exception of CVL properties. CVL will be obtained at the screening visit so that the microenvironment can recover prior to study product administration at the enrollment visit.

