#### *Nugent Score*

Clinically significant changes in vaginal flora will be evaluated by a change in the Nugent score baseline (Visit 2, pre-exposure) to Visit 5. The Nugent score is graded 1 to 10 as follows:

Normal, 0 to 3

Intermediate, 4 to 6

BV, 7-10

Any shift from normal at baseline to intermediate or BV at Visit 3 or 4, or shift from intermediate or BV to normal at Visit 3 or 4 will be considered a scientifically meaningful change in vaginal microbiota.

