The graph below plots the mean values (from 5 high power non-adjacent fields) of PMN counts for each macaque at baseline and on day 14. Both of the macaques with elevated PMN counts on Day 0 were menstruating, as was T02319 on Day 14. Clearly this film platform does not elicit a PMN response even when administered more frequently than intended. Raw data is appended.

[figure not shown]

**Vaginal pH** Super dosing with extended release vaginal films did not have a deleterious effect on vaginal pH, which normally measures 5.0-8.5 in pigtail macaques. Of four samples that measured pH 7.0 or higher in this study, three were collected during menses.

[figure not shown]
The weight and temperature of each animal also remained within normal ranges. No indication of adverse health responses to multiple film exposures were noted.

**Cervicovaginal Lavage** samples were stored at -80°C in the [name] Laboratory, then shipped to UC Denver (Core C). They will be assessed by PK analysis for polymer detection as a marker for film presence in the macaque vagina. Optimizing the conditions for PK detection of the polymer will allow future studies to include drug deposition and film platform presence to be distinguished from each other.

Two CVL samples were collected from each macaque on study day 14. One (CVL-1) was collected prior to clearing residual film for colposcopy; the second (CVL-2) was collected after removing residual film product. In addition to CVL, a sample of residual film from two macaques was frozen and provided to the PK lab.

[figure not shown]
The data from these samples will be reported separately, and are not expected to impact the safety findings.

**Colposcopy** No adverse findings were noted by colposcopy. Residual film was frequently noted. When an animal was menstruating, the residual took on a brown to red tone as seen in photos. Otherwise the residual appeared white. No formulation induced changes to the cervicovaginal tissues were noted.

Colposcopy photo plates follow.

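### The 14-day menses rule at enrollment pushes the next period towards Visit 4, which has no bleeding rule, so flora and pH changes from Visit 2 mix cycle and film effects

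*Combined protocol and SAP*

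**What the plan says.** - **Enrollment.** Exclusion 7 (section 5.5) bars bleeding at Visit 2 and also "expected menses-like bleeding within 14 days of the Enrollment visit". Section 7.3 repeats this: the visit is set for a time when the woman is "not expecting to be actively bleeding or anticipating her menses within 14 days", and "Subjects with menses like vaginal bleeding at the Enrollment visit will not be randomized/enrolled at that time".
- **Visit 4.** Section 7.5: "The final scheduled visit will be 21 (18-25) days after the Enrollment Visit". Table 5 lists pH, Gram stain, quantitative culture, qPCR, all the lavage (CVL) assays and a speculum exam. No bleeding condition, re-booking rule or specimen flag is given.
- **Baseline.** Section 9.3.2 makes each participant her own control, because there is no arm without product. "Assessment of baseline microenvironment will take place during the enrollment visit with the exception of CVL properties". For the rest, "CVL will be obtained at the screening visit so that the microenvironment can recover prior to study product administration at the enrollment visit".
- **Use of Visit 4.** For the Nugent score, "Any shift from normal at baseline to intermediate or BV at Visit 3 or 4" counts as scientifically meaningful, as does a shift the other way.
- **Analysis.** Section 9.6.3 plans McNemar, Fisher and Mann-Whitney tests for the flora measures, plus mixed models and GEE. Time since last menstrual period enters as a potential confounder.

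**The concern.** The 14-day rule spans the target days of all four Visit 3 groups, so it keeps menses out of Visit 2 and nearly all of Visit 3. The period it defers has to fall somewhere, and for a typical cycle that is the third or fourth week, where Visit 4 sits. The result is a systematic difference between visits in menstrual status, not random scatter.

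With no untreated arm, nothing in the design separates a change caused by menses from a change caused by the film. At stake is the pre/post comparison of the vaginal microbiota (section 3.3), in particular the Visit 2 to Visit 4 changes in Nugent category, culture and qPCR. The same holds for pH, which is measured at each visit although section 9.3.2 and Table 7 do not list it as an endpoint.

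Appendix IV gives some reason to expect menses to matter: "Of four samples that measured pH 7.0 or higher in this study, three were collected during menses".

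**Working it through.** The plan gives no figure for Visit 4 specimens taken in menses, so there is none to reproduce.

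**Inputs from the documents:** no bleeding at Visit 2; next onset T on day 15 or later after Visit 2; Visit 4 targeted at day 21, window 18-25 (8 days).

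**Assumptions (not in the documents):** cycle length L = 28 days (range 26-32), bleed length B = 5 days (range 3-7), and enrollment equally likely on any eligible cycle day.

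**Base case.** A woman enrolled on cycle day d has T = L + 1 - d.
- Eligible days: d above 5 (not bleeding) and T of at least 15, so d = 6 to 14 and T = 23 down to 15. That is 9 days.
- In menses on day 21 if T ≤ 21 ≤ T + 4, so T = 17 to 21. That is 5 days.
- Share: 5/9 = 56%. If onset on day 14 itself is allowed, 5/10 = 50%.

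**By cycle length (B = 5, day 21).** The eligible count is L - B - 14.

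| L | Eligible days | In menses | Share |
|---|---|---|---|
| 26 | 7 | 5 | 71% |
| 28 | 9 | 5 | 56% |
| 30 | 11 | 5 | 45% |
| 32 | 13 | 5 | 38% |

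**By bleed length (L = 28, day 21):** B = 3, 3/11 = 27%; B = 4, 4/10 = 40%; B = 5, 56%; B = 6, 6/8 = 75%; B = 7, 7/7 = 100%. Over L 26-32 and B 3-7, the extremes are 3/15 = 20% (L = 32, B = 3) and 100%.

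**Over the window (L = 28, B = 5).** On days 18 to 25 the counts out of 9 are 4, 5, 5, 5, 5, 5, 4 and 3. They sum to 36, and 36/72 = 50%.

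**With onset error.** Simulation with bleeds of 4-6 days and an error in the expected onset date of SD 0, 2 or 3 days gives 56%, 51% and 45% for a 28-day cycle. For cycles of mean 29 (SD 3) it gives 49%, 45% and 40%.

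**Visit 3 for comparison (L = 28, B = 5):** 0% through day 14, 1/9 = 11% on day 15, 2/9 = 22% on day 16.

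**Can the covariate repair it?** In the base case Visit 2 falls on cycle days 6-14. Visit 4 falls on days 27-35, that is, days 27, 28 and then 1-7. The two share only days 6 and 7. Menstrual days occur almost only at Visit 4, so the adjustment leans on extrapolation and on the assumed shape of the relation. The McNemar, Fisher and Mann-Whitney tests take no covariate at all.

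**Can the window repair it?** A bleed of B days leaves at least 8 - B free days: 3 with a 5-day bleed, 1 with a 7-day bleed.

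**The case against.** Several points on the other side stand and limit the claim.

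- **CVL.** A reader might infer that every Visit 4 measure is compared with a menses-free sample. The documents do not support that. No lavage is taken at Visit 2. The CVL baseline is Visit 1, up to 45 days before enrollment and with no stated bleeding rule. Cycle phase is uncontrolled there too, but that is a different problem.
- **Safety.** A reader might infer that blood obscures the speculum exam and so harms the primary endpoint. Nothing in the documents says this, and colposcopy was scored in menstruating macaques in Appendix IV. No effect on Grade 2 or higher adverse events is shown.
- **Half of all participants.** The figure applies to regular cyclers only. Their share is not given, and Exclusion 3h bars only diaphragm, NuvaRing and spermicide, so methods that suppress or alter bleeding are allowed.
- **Day 21 is a target.** The window exists, and section 7.7 foresees re-scheduling. Staff could avoid menses, but nothing tells them to.
- **Thin animal data.** The three samples marked as menses had pH 7.5, 7 and 7, and mean PMN counts of 11, 26.8 and 2. Of the 11 others, 10 had pH 6.5 or lower, and all had PMN of 1.4 or lower. But every pH lay within the report's normal 5.0-8.5, one non-menstruating sample also reached 7.5, and only one PMN mean exceeded the normal range of 0-15.
- **Existing handling.** Mixed models and GEE accept the planned covariate, and section 9.1 already collects menstrual symptoms.
- **Main exposure sample.** Visible film is removed at Visit 3, so that visit carries most of the film information and is largely protected. Even so, section 9.3.2 counts Visit 4 shifts as meaningful.

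**Conclusion.** The point holds for the measures baselined at Visit 2: Gram stain/Nugent, culture, qPCR and pH. Followed as written, the plan samples about half of regularly cycling women in menses at Visit 4 against a menses-free baseline: 56% at day 21 for a 28-day cycle and 5-day bleed, and about 40-56% with bleeds of 4-6 days and onset error. The full range is 20-100%, because cycle and bleed lengths are assumptions. At a 50% share among cyclers, that is 0.5 × 64 = 32 women if all cycle regularly and 0.5 × 32 = 16 if half do; the proportion who cycle is also an assumption.

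The planned covariate is a partial remedy. The affected analyses are exploratory, and the primary endpoint and its sample size are untouched. The change is still worth making, because the confound is predictable and cheap to avoid.

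**What to change.** - **Section 7.5:** state that Visit 4 is booked, within the existing 18-25 day window, on a day when menses-like bleeding is not expected, and re-booked within the window if the participant is bleeding.
- **Data collection:** record bleeding at every sampling visit, including Visit 1 for the CVL assays, and flag the specimens concerned.
- **Section 9.6.3:** run the pre/post microenvironment analyses with and without specimens taken during bleeding.

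**Cost.** One scheduling sentence, one data field and one sensitivity analysis. Some visits will be re-booked, and Visit 4 will spread over its window instead of clustering at day 21. With a 7-day bleed as few as 1 of the 8 window days is free, so some bleeding specimens will remain, which is why the flag is needed. In the Day 14 group, Visit 3 may be as late as day 16 and Visit 4 as early as day 18, only 2 days after a lavage, while section 9.3.2 treats recovery after lavage as necessary. In that group a later bleed-free day should be used when one is available.
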